Due to the increasing concern regarding patient satisfaction with medical care and the documented association between satisfaction and treatment adherence (Lochman, 1983), patient satisfaction has been included as a secondary outcome. A 9-item self-administered questionnaire has been developed to assess this outcome. These items measure patient satisfaction with the result of surgery related to activities previously restricted by UI symptoms and to emotions associated with UI, as well as providing a measure of patients' global sense of satisfaction with the outcome. Because it has been established that treatment satisfaction is affected by the patient's pre-treatment expectations of the outcome (Mancuso, Salvati, Johanson, Peterson, & Charlson, 1997; Williams, Weinman, Dale, & Newman, 1995; Wilson, Saling, Kincade, & Bladin, 1998), an accompanying measure of treatment expectations has also been developed. The 10-item self-administered questionnaire measures expectations of improvement in UI symptoms, improvement in activities limited by UI, and improvement in emotions associated

with UI. Both of these measures are currently being tested for validity and reliability at the University of Pittsburgh.

H.3 Independent Variables

There are four groups of independent variables:

- *Sociodemographic characteristics*: age; race; marital status; education; occupation; annual income; insurance status
- *Risk factors for UI*: age (Milsom, Ekelund, Molander, Arvidsson, & Areskoug, 1993; Yarnell, Voyle, Richards, & Stephenson, 1981); parity (Burgio, Locher, Zyczynski, Hardin, & Singh, 1996; Foldspang, Mommsen, Lam, & Elving, 1992; Jolleys, 1988; Sommer et al., 1990; Thomas, Plymat, Blannin, & Meade, 1980; Yarnell, Voyle, Richards, & Stephenson, 1982); weight of largest baby; menopause status and use of HRT (Burgio et al., 1991; Jolleys, 1988); BMI (Brown et al., 1996; Burgio et al., 1991; Mommsen & Foldspang, 1994; Yarnell et al., 1982); previous anti-incontinence and gynecologic surgery (Jolleys, 1988; Milsom et al., 1993); current medications (Montella & Wordell, 1996)
- *Type and severity of UI* measured by the following: MESA questionnaire (Herzog et al., 1990); stress test; Q-Tip Test; Pad Test; Voiding Diary; Urodynamic Studies (i.e., uroflowmetry; cystometrogram; pressure flow study)
- *Urodynamic Studies*, including uroflowmetry; cystometrogram; pressure flow studies

H.4 Intervening Variables

Intervening variables that might affect the outcomes of interest consist of the following four categories:

- *Pelvic comorbidity*: pelvic organ prolapse (POP-Q quantification)
- *Intraoperative considerations*: surgical and medical complications (see Appendix B); length of procedure; estimated blood loss (see Appendix C)
- *Postoperative considerations*: length of hospital stay; post-operative pain; medical complications (e.g., pulmonary, febrile morbidity, cardiovascular, neurologic, urinary tract; see Appendix B); de novo or recurrent urinary urgency or urge incontinence; other non-surgical treatments
- *Patient expectations of surgery*

H.5 Schedule of Measurements

The schedule of measurements is included in Appendix A. Data will be collected during clinic visits at baseline, 6-weeks, 6-months, 12-months, and 24-months, and by mail or telephone at 3-months and 18-months.

For those patients determined to be a treatment failure because of surgical retreatment for SUI, the 24-month assessment battery will be completed at the time that this surgical retreatment is determined necessary (i.e. before the surgical retreatment). Follow-up visits will continue as scheduled with one exception to the assessment battery at 24 months, i.e. UDS will not be required at 24-months as testing was conducted prior to surgical retreatment. For those patients determined to be a treatment failure for all other reasons, the 24-month assessment battery will be completed at the time that this treatment is determined necessary, but further follow-up assessments will continue as scheduled. If the

out-of-sequence 24-month assessment is performed within the specified window for the next assessment, then that next assessment can be omitted.

If more than 6 months transpires between determination of eligibility and surgery, the following measures must be repeated to ensure current eligibility for the trial as well as to obtain current baseline values for critical measures that would be subject to change over a 6-month period.

- 1) The MESA assessment (Data Form 01, Sections C and D),
- 2) Recent pelvic surgery (Data Form 02, Section C),
- 3) Medication Audit (Data Form 03),
- 4) POP-Q examination (Data Form 04, Section E),
- 5) The Pad Test (Data Form 06, Section B),
- 6) The Voiding Diary (Data Form 06, Section C),
- 7) Expectations of Surgery (Data Form 07, Section B),
- 8) Quality of Life (Data Form 07, Section C),
- 9) Normal Activities (Data Form 07, Section D),
- 10) Sexual Function (Data Form 07 Section E), and,
- 11) All other eligibility criteria that might be subject to change over a 6-month period including:
 - Current UTI,
 - Pregnancy status (Data Form 01, Section E & Form 04 Section H),
 - Recent diagnosis of lower urinary tract cancer, Parkinson's Disease, multiple sclerosis, spinal cord injury or trauma (Data Form 02, Section B),
 - Report or evidence of urethral diverticulum, prior augmentation cystoplasty or artificial sphincter (Data Form 02, Section B, & Form 04, Section H),
 - Current intermittent catheterization (Data Form 02, Section B),
 - Current cancer chemotherapy or radiation therapy (Data Form 02, Section B),
 - ASA classification (Data Form 04, Section H),
 - Candidate for harvesting of autologous rectus fascia graft (Data Form 04, Section H).

The UDS, Q-Tip Test and the Stress Test do not have to be repeated.

I. TESTING PROCEDURES

I.1 Physical Exam and History

The following data will be collected from the pre-operative history and physical examination.

a. History:

- age
- race
- pregnancies (parity, weight of largest baby, number of vaginal deliveries)
- past pelvic surgeries
- history of estrogen replacement therapy
- duration of incontinence
- smoking history
- occupational history
- past surgical and medical incontinence treatments

- frequent UTIs, defined as >3 in previous 12 months
- bowel function, including fecal incontinence

b. Examination:

- height and weight (for BMI)
- directed neurological exam: to be recorded as present/absent OR normal/decreased:
 - deep tendon reflex knee
 - perineal sensation
 - anal sphincter voluntary contractions
- strength of pubococcygeus muscle (9-point scale based on strength, duration and movement observed with muscle contraction; (Brink, Well, Sampsel, Taillie, & Mayer, 1994))

c. Q-Tip Test

The Q-Tip Test (Crystie, Charme, & Copeland, 1971) will be used to quantify bladder neck mobility using a standardized procedure as described in the Physical Examination Procedures Manual.

d. Pelvic Organ Prolapse Quantification (POP-Q)

The pelvic organ prolapse evaluation will be performed according to the guidelines established by the International Continence Society (Bump et al., 1996). The procedure will be standardized as demonstrated in a videotape produced by Duke University Medical Center (“Pelvic Organ Prolapse Quantification Examination”) and described in the Physical Examination Procedures Manual.

e. Provocative Stress Test

A standardized provocative stress test procedure will be performed for eligibility determination as described in the Stress Test Procedures Manual.

I.2 Pad Test

The Pad Test will be 24-hours in duration. All sites will use the same materials (pads and biohazard plastic zip-lock bags) and the same brand/model of scale for weighing the pads. All pads will be weighed individually in their biohazard bags.

The Pad Test will be done over a 24-hour period during the three voiding diary days. The only data to be collected will be the number and weight of pads worn by the patient. Pad Test instructions for patients will be provided on a videotape produced for this purpose.

I.3 Urodynamic Studies (UDS)

The order and procedures for urodynamic testing and the required measures of standardization are covered in detail in the UDS Procedures Manual in the Manual of Operations. UDS will be conducted at baseline and at 24-months post-surgery. The treating MD might decide to conduct UDS earlier than 24-months if a patient complains of, or has evidence of, voiding difficulties/dysfunction. However, follow-up UDS will be conducted no earlier than 4-weeks post-operatively as any voiding dysfunction during that time would fall under the definition of temporary.

Two additional timepoints at which UDS is required are as follows: 1) If a patient is going to have surgery post-UITN surgery for voiding dysfunction, it is required that the Investigator conduct UDS on the patient prior to that surgery; 2) If a patient is deemed a “treatment failure” prior to 24 months post-op, UDS will be conducted (along with the entire 24 month battery) at that time.

J. ADVERSE EVENT REPORTING AND THE DSMB

Adverse events (AEs) will be reported in accordance with the Department of Health and Human Services (DHHS) code of federal regulations (Title 45, Part 46). (<http://ohrp.osophs.dhhs.gov/humansubjects/guidance/45cfr46.htm>). As required, a Data and Safety Monitoring Board (DSMB) has been organized. The DSMB is scheduled to meet every 6 months, once by teleconference and once in-person in a 12-month period.

Adverse events, defined as “unanticipated problems,” have been specified for this trial. The list of reportable AEs was approved by the DSMB and is provided in Appendix B and at the bottom of the Adverse Event Form. There are two categories of AEs: 1) Serious Adverse Events and 2) Adverse Events. Serious adverse events are required to be reported to the BCC and NIDDK within 72 hours of occurrence or knowledge of the event. Adverse events not in the “serious” category, but judged to be “severe” or “life threatening” are also subject to the 72 hour reporting requirement. This reporting requirement is met by completing an Adverse Event Form and faxing it to the BCC and NIDDK. Copies of reports of all SAEs will be forwarded to the Chairperson of the DSMB.

At the bi-annual meetings of the DSMB, summary reports of all reportable AEs will be reviewed. The BCC is responsible for preparing these summary reports. Interim monitoring by the DSMB is also discussed in Section K2. After review, the Executive Secretary of the UITN DSMB is responsible for generating a brief summary report for distribution to all clinical sites, the BCC, and NIDDK. The report will document that a review of data and outcomes across all centers took place on a given date. It will also inform Investigators of the DSMB’s conclusion with respect to progress or need for modification of the protocol. Investigators are required to submit a copy of this report to their local IRB. If there is any correspondence with the DSMB outside of the planned meetings that has study-wide implications, it is the responsibility of the Executive Secretary of the UITN DSMB to draft an appropriate memo for distribution to all clinical sites, the BCC, and NIDDK. Again, Investigators are responsible for submitting a copy of this correspondence to their IRB.

K. STATISTICAL CONSIDERATIONS

K.1 Sample Size Determination for Primary Endpoints

Two primary endpoints will be used: 1) “overall treatment success” to evaluate a broadly defined pragmatic benefit of surgery and 2) “treatment success specific to SUI” to evaluate a more narrow and mechanistic measure of benefit. See Section D for criteria. The primary time point for evaluating success is at 24-months. Although these measures of success cannot be fully documented until 24-months, a failure can be documented earlier (if, for example, a patient requires surgical treatment or has a positive stress test at 12-months).

Because the urge component of incontinence in women with mixed incontinence is not expected to be improved by either surgical procedure being studied, the requirement of negative self-report and negative pad test may prevent women from achieving the clinical endpoint of "overall treatment success" even if the surgery is successful in eliminating the stress component of incontinence. Therefore, although many reports of both Burch and sling procedures suggest "success" rates of approximately 80-85%, we expect to observe lower success rates in this trial, by approximately 15-20 percentage points. A sample size of 260 per group, or 520 total, would

ensure 80% power to detect a 12 percentage point difference (60% vs. 72%) using a two-sided $\alpha=.05$ Fisher's exact test. In order to meet the criteria for success, patients must be willing to undergo a fairly intensive measurement process (self-administered questionnaire, 3-day diary, 24-hour pad test, stress test). It seems likely that some women who consider themselves to be cured will not comply with this regimen. Therefore, to adjust for a 20% non-compliance rate, the target sample size will be inflated to 325 per group, or 650 total.

For the more mechanistic endpoint, “treatment success specific to SUI,” we assume a higher success rate, i.e., >80%. The target sample size will ensure >85% power for detecting a 10 percentage point difference (80% vs. 90%).

K.2 Interim Monitoring

Ordinarily, early stopping rules are based on monitoring the primary endpoints for a treatment difference so large that it is unethical to continue treating one group of patients with the “inferior” treatment, and on monitoring the treatments for safety. In this trial, however, several considerations argue against the usual motivations for early stopping procedures.

First, we expect very little primary endpoint data to be available while any participants are still at risk for exposure to either surgery being evaluated. Accrual is expected to take 24-months and success on the primary endpoints is not documented until 24-months after surgery. Therefore, at the time the first participants are reaching the assessment time for documenting “success”, all or nearly all patients will already have had their surgery. Nevertheless, there will be some information on the primary endpoints prior to 24-months, since self-reported stress-type symptoms, a positive diary, positive pad test or positive stress test at 6-24 months, or retreatment for SUI at any time prior to 24-months will be considered a failure.

Second, both the Burch modified Tanagho and the autologous fascia sling procedures are “standard” surgical procedures. Unlike a trial evaluating a new surgical procedure, the study procedures in this trial have generally well-known complications. It is unlikely that we will experience any new or unexpected complications. Of course, we will collect and document complications but we do not expect that treatment group differences in surgical complication rates would pose an ethical imperative to stop the trial, unless some serious unexpected complication is prevalent. Rates of the more serious surgical complications (e.g. organ damage, sling erosion, hernia, wound infection) will be summarized separately within each site and further within each surgeon, to monitor for problems with specific hospitals or surgeons.

Formal interim data monitoring will be based on a time-to-event analysis, specifically a logrank test, with the event defined as failure of the primary endpoint, as defined in Section D. With an anticipated 60-72% success rate, we expect about 35% of patients to “fail”, or about 200 failures. Formal interim hypothesis testing will be performed after approximately 50, 100, and 150 failures have occurred. The methodology of Lan and DeMets will be used to implement an O’Brien-Fleming stopping boundary for this monitoring. The Lan and DeMets methodology allows flexibility in the exact timing of the interim analyses, so that for example a DSMB meeting can be scheduled for when approximately 50 failures are expected to have occurred, but if the actual count is not exactly 50, the stopping boundary can be adjusted accordingly. The O’Brien-Fleming boundary is probably the most commonly used stopping boundary because it is conservative early in the trial (i.e. a very strong treatment difference is required for stopping) but maintains close to the nominal significance level toward the end of the trial (i.e. almost any p-value less than .05 at the end of the trial can be considered “significant”).

In addition, treatment differences for any endpoint significant at the .001 level will be brought to the attention of the DSMB for consideration of possible early stopping.

Any early stopping boundary should be considered a guideline and not a hard-and-fast rule. Instead, the evidence should be considered in the context of other study data. Accordingly, DSMB reports will ordinarily include summaries of a variety of endpoints, patient characteristics, adverse events, data quality, and any unanticipated problems that arise during the conduct of the trial.

K.3 Analytic Approach

Fisher's exact test will be used for unadjusted analysis of the primary endpoints and other dichotomous outcomes (e.g. complication rates). Time-to-failure analyses (Kaplan-Meier plots and logrank tests) will also be used in secondary analyses of the primary outcome as described above under "Interim Monitoring." Treatment comparisons will be adjusted for covariates with the logistic model for dichotomous endpoints and proportional hazards models for time-to-failure analyses. Analysis of continuous outcomes such as the quality of life subscales will be based on change from baseline. Prognostic models will be developed using baseline urodynamic testing results and other baseline covariates to explore the extent to which baseline measures can be used to predict surgical success. Time-to-event methods will be utilized to characterize time to normal voiding. In addition to comparing treatment groups with respect to satisfaction with surgery, the analysis of this outcome will include an evaluation of expectations of surgery as a predictor of satisfaction.

L. RECRUITMENT

To assess ability of the nine clinical centers to enroll the required number of patients (73 patients per center) into the trial over a two-year period, each center provided data in July 2001 regarding the number of Burch and sling procedures performed over the prior 12-months. These data are displayed in Table 2. Based on these data and the estimated enrollment rate of 20% of eligible patients, there appear to be a sufficient pool of patients from which to recruit. In the event that the enrollment rate has been overestimated (i.e. fewer patients agree to participate in the trial), several additional sources of potential patients have been identified:

- Investigator's office (might include patients of a non-study surgeon in a group practice);
- Referrals from colleagues;
- Post-card announcements in clinical areas/offices;
- Advertising: newspapers; newsletters; cable TV or public service announcements; websites of professional organizations, advocacy groups, or NIH; health fairs, health clubs, billboards;
- Mailings to enriched lists, e.g., former patients.

Table 2. Number of Procedures by Site: Approximate 12 Months prior to July 2001

Site	Burch	Sling
University of Alabama - Birmingham	68	162
University of California - San Diego	123	152
University of Maryland	46	155
University of Pittsburgh	33	297
University of Texas - Dallas	141	102
University of Texas - San Antonio	5	93
University of Utah	636	65
Beaumont Hospital	89	163
Loyola University	*	*
Total	1141	1189

*Not a participating center at time of survey

M. INFORMED CONSENT PROCEDURES

It is expected that patients will undergo clinical assessment for type of urinary incontinence and candidacy for surgery. If a patient appears to be eligible for the study, including eligibility for either a Burch or sling procedure, she will be approached about the study. The patient will be asked to view a videotaped description of the trial (presented by the Steering Committee Chair, [name]) and then will be presented with the informed consent form by study personnel, either the surgeon or research nurse. Written informed consent will be obtained prior to proceeding with any further eligibility determination, testing, or data collection activities.

Templates for the informed consent forms will be used by all of the centers, modifying the content or format as necessary to meet the requirements of their respective institutional human subjects committees.

N. DATA MANAGEMENT

A customized data management system (DMS) has been developed for this study using the Biostatistical Coordinating Center's Web-based Advanced Data Entry and Protocol Tracking (ADEPT) system. ADEPT integrates all aspects of study data collection including: participant screening and enrollment data; real time accrual reporting; tracking of participant study appointments for follow-up; all study follow-up data collection; censoring/loss to follow-up data; and monitoring timeliness and quality of data collection. Data are stored in an Oracle relational database at the BCC. CTCs enter data via a customized ADEPT secure web application that provides real-time field level validations and context sensitive help. HTML data entry forms are enhanced with client side JavaScript code to ensure rapid entry of study forms, proper validations of all data fields and proper skip patterns within study data forms. Interim background data submittals prevent loss of data due to loss of internet connections.

N.1 Data Entry

ADEPT includes a number of standard features designed to ensure consistently high quality data. Integrated into the data entry system are real time validations, including both inter- and intra-instrument data checks. Inconsistent or questionable values are flagged during entry, and an edit report is automatically generated. These edit reports are designed to be human readable, listing the participant ID, the instrument name, and a detailed description of why each

specific data item was flagged. The edit report can be printed out and reviewed by a supervisor or returned to the data collector for resolution. The ADEPT system also tracks missing data rates by instrument and data collector. Data entry quality is monitored through a sample-based double data entry system. A self-adjusting algorithm is used to enforce a higher double data entry rate on keyers who have higher error rates.

N.2 Data Security and Integrity

The web based components of the data management system utilize several levels of security to ensure privacy and integrity of the study data:

- Web Access requires use of assigned user names and passwords.
- Passwords will be changed every 90 days.
- Web based entry uses secure socket layer data encryption.
- Firewall protects against unauthorized access to study data.

All study data will be stored on the BCC's NT based Oracle server. Access to data on this server (from both inside and outside the data center) is controlled by Oracle's extensive security features. Oracle archiving and backup system ensures minimal data loss even in the most catastrophic system failure. Backup data tapes are stored off site in a nearby bank safety deposit box.

O. QUALITY CONTROL ACTIVITIES

The BCC has primary responsibility for QC/QA activities. The BCC also requires that the sites complete certain QC activities, most of which are monitored by the BCC.

The key QC/QA activities are:

- Development of a study Manual of Operations as well Procedures Manuals (for surgical procedures, urodynamic studies, other physical tests)
- Clearly formatted and carefully constructed Data Forms, clearly linked to the research questions and research models, with clear, up-to-date manuals of instruction;
- Sign-Off Procedures for all study forms;
- Central training, with hands-on practice and certification, of all CTC data collection staff with the use of standardized checklists;
- Certification of all participating surgeons in the surgical procedures;

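### K.1 names two primary endpoints and gives the whole two-sided .05 to the first, but no rule links them; if either could carry the claim, the family-wise error is about 6–7%

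*Protocol*

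**What the plan says.** - **Two primaries.** K.1: "Two primary endpoints will be used". The first is overall treatment success, described as pragmatic. The second is treatment success specific to SUI, described as mechanistic.
- **Sizing.** K.1 takes 260 evaluable women in each arm as the number needed to "ensure 80% power to detect a 12 percentage point difference (60% vs. 72%) using a two-sided $\alpha=.05$ Fisher's exact test". Then, "to adjust for a 20% non-compliance rate, the target sample size will be inflated to 325 per group, or 650 total".
- **Second endpoint.** K.1: "The target sample size will ensure >85% power for detecting a 10 percentage point difference (80% vs. 90"%). No alpha is given in that sentence.
- **Final test.** K.3: "Fisher's exact test will be used for unadjusted analysis of the primary endpoints", in the plural.
- **Final level.** K.2, on the O'Brien-Fleming boundary: "almost any p-value less than .05 at the end of the trial can be considered" significant. The boundary is applied to failure of a single primary endpoint. The success rates quoted there, 60–72%, are those of overall success.
- **Definitions.** In Section D, overall success requires every SUI-specific criterion plus a negative pad test and a dry diary.

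No section gives a testing order, a division of alpha, or a rule that both endpoints must be significant.

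**The concern.** The first endpoint alone uses the whole 5%. Whatever alpha the second receives takes the nominal total above 5%, unless a rule ties the two together. The interim boundary is not such a rule: it controls repeated looks at one endpoint, not the choice between two.

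The practical risk is a split result. The endpoints differ only by the diary and pad components, and K.1 itself expects women with an urge component to fail overall success while their stress leakage is cured. If one endpoint gives p<.05 and the other does not, the protocol does not say what the trial concludes, and the choice would be made with the data in view.

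**Working it through.** **1. The plan's own figures reproduce.** For 60% vs 72%, two-sided .05, 80% power:

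n = [1.96·√(2·0.66·0.34) + 0.8416·√(0.60·0.40 + 0.72·0.28)]² / 0.12² = (1.3131 + 0.5593)² / 0.0144 ≈ 243.5, i.e. 244.

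With continuity correction: (243.5/4)·[1 + √(1 + 4/(243.5·0.12))]² ≈ 260. Inflation: 260/0.80 = 325. The sizing arithmetic is correct.

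**2. Which alpha does the second power figure imply?** Exact Fisher power:

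| n per group | alpha | 60% vs 72% | 80% vs 90% |
|---|---|---|---|
| 260 | .05 | 80.0% | 87.4% |
| 260 | .025 | 71.4% | 80.8% |
| 325 | .05 | 88.6% | 93.9% |
| 325 | .025 | 82.0% | 89.8% |

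K.1 attaches the figure of more than 85% to the target sample size, which the preceding sentence sets at 325 per group. There both .05 and .025 satisfy it, so the figure does not identify the alpha.

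**3. Family-wise error if either endpoint at p<.05 were enough.** Inputs: equal arms; Fisher's test at two-sided .05 on each endpoint; null success rates assumed from the planning ranges. Overall success implies SUI-specific success, so the correlation follows from the rates: φ = √[p_o(1−p_s)/(p_s(1−p_o))]. At 66% and 85%, φ = √(0.66·0.15/(0.85·0.34)) = 0.585. Simulated chance of at least one false positive:

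| Null rates (overall / SUI) | φ | 260 per group | 325 per group |
|---|---|---|---|
| 72% / 80% | 0.80 | 6.2% | 6.4% |
| 66% / 85% | 0.59 | 6.8% | 7.1% |
| 60% / 80% | 0.61 | 7.0% | 7.1% |
| 60% / 90% | 0.41 | 7.3% | 7.3% |

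Runs differ by about 0.1 point, so the range is quoted as 6.2% to 7.4%. Independent tests would give 1 − 0.95² = 9.75%. The figure is lower here because the endpoints are nested and because each Fisher test has a true size of only about 3.6–4.2%.

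**4. How often the endpoints disagree.** Under the protocol's alternatives (60/72 and 80/90 together), at 260 per group: both significant 74.3%, SUI-specific only 13.1%, overall only 5.7%. Exactly one is therefore significant in about 19% of trials (about 12% at 325).

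**5. What each linking rule costs (Fisher's test).**

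| Rule | Overall, 260 | SUI-specific, 260 |
|---|---|---|
| None (.05 each) | 80.0% | 87.4% |
| Fixed order, overall first | 80.0% | about 74% |
| Hochberg, both alternatives true | about 78% | about 85% |
| Hochberg, only overall differs (SUI equal at an assumed 85%) | 71.5% | – |
| Hochberg, only SUI differs (overall equal at an assumed 66%) | – | 81.1% |
| Bonferroni | 71.4% | 80.8% |

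Under the fixed order, a SUI-specific claim needs both tests significant, so its power is the 74.3% in step 4 (about 85% at 325). To restore 80% for overall success under Bonferroni takes 312 evaluable per group, and 312/0.80 = 390 enrolled.

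All these figures use .05 and .025 without the reduction for interim looks, which K.2 describes as slight.

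**The case against.** The best reply is that a multiplicity rule commonly sits in the SAP, which is not shown. Nothing in K.1 to K.3 rules out a fixed order, and that would hold 5% with no change in sample size. There are signs that an order is intended: K.1 numbers the endpoints, sizes the trial on the first, and K.2 monitors at the rates of overall success; Section D introduces the SUI-specific outcome as a second definition. This lowers the severity but does not remove the point. K.1 has already committed the full .05 to the first endpoint and quotes a power for the second. Every linking rule changes at least one of those powers, so the rule belongs beside them.

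A reader might also infer more than the text supports:

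- **That both endpoints are expressly planned at .05, as the second power figure shows.** At 325 per group, .025 also gives about 90%. The .05 is an inference from K.2 and K.3.
- **That the trial would declare superiority on either endpoint.** No such rule is written. The primary aim in Section A joins the two outcomes without saying how they combine.
- **That the error is near 9–10%.** At 66%/85%, a test with true size .05 on each endpoint would give 8.8%, but the protocol specifies Fisher's test, which gives about 6.8%. Each endpoint taken singly stays below 5%.
- **That leaving the second endpoint out of interim monitoring adds further inflation.** An endpoint with no formal interim test spends no alpha at those looks.

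**Conclusion.** The point holds in limited form. The protocol declares two primary endpoints, commits the whole two-sided .05 to the first and states no rule that links them. If significance on either were taken as a confirmatory result, the family-wise error would be about 6–7%, an excess of roughly one to two and a half points. It is above 5% in every scenario tried.

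This rests on three assumptions: a .05 level for the second endpoint, null rates within 60–72% and 80–90%, and the same women evaluable for both endpoints. The lack of a stated conclusion for split results depends on none of them, and is the more practical defect. This should be fixed, but it does not undermine the sample size, which is correct for the first endpoint.

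**What to change.** Add to K.1 and K.3: overall treatment success is tested first; treatment success specific to SUI is tested confirmatorily only if overall success is significant; each test uses the two-sided .05 final level left by the interim boundary. If overall success is not significant, the SUI-specific result is reported as descriptive.

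The cost is a few sentences. The sample size and the 80% power for overall success do not change. K.1 should state the price: no confirmatory SUI-specific claim if overall success fails, and power for that claim of about 74% at 260 evaluable per group (about 85% at 325) under the protocol's alternatives, in place of the present figure.

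Hochberg is an acceptable alternative if the sponsor wants either endpoint to be able to carry a claim. Its cost must then be given in full: about 2 points on each endpoint if both alternatives hold, but about 8 points on overall success (80% to 71.5% at 260 per group) if only that endpoint differs.
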